10 WITHDRAWAL

In accordance with the Declaration of Helsinki⁵⁶, the ICH Tripartite Guideline for GCP Topic E6(R2)⁵², the U.S. FDA regulations relating to good clinical practice and clinical trials^{57,58,59}, the European Union (EU) Clinical Trials Directive⁶⁰, the EU Good Clinical Practice (GCP) Directive⁶¹ and/or other applicable regulations, a patient has the right to withdraw from the study at any time and for any reason without prejudice to his or her future medical care by the physician or at the institution.

The patient must be withdrawn from the study if any of the following apply:

- Administrative decision by the investigator, GW, or a Regulatory Authority.
- Pregnancy.
- Protocol deviation that is considered to compromise potentially the safety of the patient.
- Withdrawal of patient consent/assent.
- Withdrawal of parent(s)/legal representative consent.
- ALT or AST > 3 × ULN with the appearance of fatigue, nausea, vomiting, right upper quadrant pain or tenderness, fever, rash, and/or eosinophilia (> 5%).
- ALT or AST > 8 × ULN.
- ALT or AST > 5 × ULN for more than two weeks.
- ALT or AST > 3 × ULN **and** (TBL > 2 × ULN **or** INR > 1.5).
- Lost to follow-up.

Note: Prior to withdrawal for the transaminase elevations noted above, the investigator may choose to confirm the transaminase elevations by repeating the following laboratory tests within 24 to 48 hours: ALT, AST, TBL, INR, %eosinophils, gamma-glutamyl transferase and alkaline phosphatase. Should the above transaminase elevation criteria be confirmed, the patient must be withdrawn from the trial. In cases where the transaminase elevation withdrawal criteria are not met or confirmed, the dose of IMP or a concomitant AED with known hepatotoxicity should be reduced following discussion with the GW medical monitor.

Study Code: GWEP1521
EudraCT Number: 2015-002154-12
Protocol V8 23Apr19

Patients may also be withdrawn from the study for any of the following:

- Did not meet eligibility criteria.
- Patient non-compliance.
- AE (including clinically significant laboratory result) which, in the opinion of the investigator, would compromise the continued safe participation of the patient in the study.
- Suicidal ideation or behavior of type 4 or 5 during the treatment period, as evaluated with the C-SSRS.
- Any evidence of drug abuse or diversion.
- General anesthesia (blinded phase only).
- Addition of a new AED (blinded phase only).

Should a patient request or decide to withdraw from the study, all efforts must be made to complete all assessments of the End of Treatment/Withdrawal Visit (see [Section 9.1.1.10](#) for withdrawals within the double-blind phase and [Section 9.1.2.10](#) for withdrawals within the OLE phase). All observations should be reported as thoroughly as possible up to the date of withdrawal. Patients withdrawing due to an AE should be followed up according to [Section 12.7](#). All information should be reported in the applicable CRF pages (refer to [Section 9.2](#)). Wherever possible, a post-study follow-up visit should take place 28-days after last dose of IMP (refer to [Section 9.1.1.12](#) and [Section 9.1.2.13](#)). If withdrawing patients decline to give a reason for withdrawal of consent, the investigator must respect the patient's wishes.

Study Code: GWEP1521
EudraCT Number: 2015-002154-12
Protocol V8 23Apr19

11 URGENT SAFETY MEASURES

The sponsor and investigator may take appropriate urgent safety measures in order to protect the patients of a clinical trial against any immediate hazard to their health or safety. If such measures are taken by the investigator they must notify GW immediately or at least within 24 hours of awareness. GW will report urgent safety measures to Regulatory Authorities by telephone within 24 hours of awareness, wherever possible, and will provide a written report to the Regulatory Authorities and EC/IRB within three days.

Study Code: GWEP1521
EudraCT Number: 2015-002154-12
Protocol V8 23Apr19

12 ADVERSE EVENT REPORTING

12.1 Definitions

12.1.1 Adverse Event

For the purposes of this study an AE is defined as:

Any new unfavorable/unintended signs/symptoms (including abnormal laboratory findings when relevant), or diagnosis or worsening of a pre-existing condition, which occurs following screening (Visit 1) and at any point up to the post-treatment, safety follow-up visit (Visit 12 and Visit OLE Follow-up), which may or may not be considered to be related to the IMP. Any event that is the result of a study procedure must be recorded as an AE.

Surgical/Investigational procedures are not AEs. The medical reason for the procedure is the AE. Elective hospitalizations for pre-study existing conditions or elective procedures are not AEs. The exception may be if the patient has an AE during hospitalization which prolongs their scheduled hospital stay in which case it would be considered a SAE (refer to [Section 12.2](#)).

If reporting a fatal event, the SAE term should be the underlying cause of the death (e.g., disease or medical condition leading to death).

12.1.2 Investigator

The term investigator refers to the study PI or a formally delegated study physician.

12.2 Serious Adverse Events

During clinical investigations, AEs may occur which, if suspected to be IMP-related, might be significant enough to lead to important changes in the way the IMP is developed (e.g., change in dose, population, monitoring need, consent/assent forms). This is particularly true for events that threaten life or function. Such SAEs will be reported promptly to Regulatory Authorities, applicable ECs/IRBs and investigators (expedited reporting) by GW.

An AE must only be classed as serious, i.e., a SAE, when the event falls into one of the following criteria:

- Results in death.
- Is life-threatening*.

Study Code: GWEP1521
EudraCT Number: 2015-002154-12
Protocol V8 23Apr19

- Requires inpatient hospitalization or prolongation of existing hospitalization.
- Results in persistent or significant disability/incapacity.
- Is a congenital anomaly/birth defect.
- Is medically significant**.

* The term “life-threatening” in the definition of “serious” refers to an event in which the patient was at risk of death at the time of the event; it does not refer to an event which, hypothetically, might have caused death if it were more severe.

** Medical and scientific judgment should be exercised in deciding whether SAE reporting is appropriate in other situations. Important medical events may not be immediately life-threatening or result in death or hospitalization but may jeopardize the patient or may require intervention to prevent one of the other outcomes listed in the definition above. These should also usually be considered serious. Examples of such events are intensive treatment in an emergency room or at home for allergic bronchospasm, blood dyscrasias or convulsions that do not result in hospitalization, or development of drug dependency or drug abuse.

The sponsor considers all convulsive and non-convulsive *status epilepticus* events to be medically significant and should be reported to the Sponsor as medically significant SAEs.

12.3 Reporting Procedures for Serious Adverse Events

All SAEs occurring during the study must be reported to GW with any other supporting information and recorded in the AE section of the CRF. Any ongoing SAEs should be followed up until resolution wherever possible. For all deaths, the working diagnosis or cause of death as stated on a death certificate, available autopsy reports and relevant medical reports should be sent to GW promptly.

All SAEs must be reported directly to the GW PVD within 24 hours of discovery or notification of the event. All SAE information must be recorded in the SAE Report forms provided in the center files and faxed to the GW PVD. Additional information received for a case (follow-up or corrections to the original case) need to be detailed on a new SAE Report form, signed/dated and faxed to the GW PVD and the AE section of the CRF must be updated.

The investigator is not obliged to actively monitor for any new SAEs which occurred after the last formal follow-up observational period (Visit 12 or OLE Follow-up).

Study Code: GWEP1521
EudraCT Number: 2015-002154-12
Protocol V8 23Apr19

However, if the investigator becomes aware of any deaths or a new IMP-related SAE occurring within 28 days of the final dose of IMP, these should be reported to the GW PVD.

Any other problem discovered outside these time limits (Visit 12 or OLE Follow-up) which is deemed to be an unexpected safety issue and is likely to have an impact on patients who have taken part in the study must be treated as an SAE and reported to the GW PVD. Such post-study SAEs do not need to be recorded in the patient's CRF if editing rights to the CRF have been removed due to final study data lock. GW PVD may request safety follow-up information after the final study visit in order to investigate a potential safety issue.

Contact details for the GW PVD are provided at the front of the center files for all study centers, and upon the GW SAE Report form.

12.4 Pregnancy

Any patient, or patient's partner, who has become pregnant whilst receiving IMP, or within 90 days of last dose of IMP, must be reported to the GW PVD, using the GW Pregnancy Monitoring forms provided. Where possible the investigator should provide the outcome of the pregnancy.

Pregnancy reports must be sent to the GW PVD using the fax number for SAE reporting (see Appendix 3.2) within 24 hours of becoming aware.

The investigator is not obliged to actively monitor for any pregnancies that commence more than 90 days after the final dose of IMP. However, if the investigator becomes aware of a new pregnancy outside this time limit then they should report it as above. The GW PVD will follow up for all pregnancy outcomes.

12.5 Causality Assessment

Causality assessment is required for all AEs and SAEs. Causality assessment must only be assigned by the investigator. All cases judged as having a reasonable suspected causal relationship to the IMP must be reported as such. The expression "*reasonable causal relationship*" is meant to convey in general that there are facts (evidence) or arguments to suggest a causal relationship.

The following question which must be answered by the investigator for all AEs is used to capture the reasonable causal relationship of an event to the IMP:

"In your opinion is there a plausible relationship to the IMP?" The answer is either "yes" or "no".

Study Code: GWEP1521
EudraCT Number: 2015-002154-12
Protocol V8 23Apr19

Events that start before the first dose of IMP (pre-treatment) should be considered as not causally related. Where a pre-treatment event worsens in severity following the first dose of IMP, a new event record should be entered into the CRF.

Considering the explanation given above, investigators are strongly encouraged to express their opinion on what the cause of an AE might be. For individual patients, the investigator is usually in the best position to assess the underlying suspected cause of an AE. For all AEs, and especially SAEs, it is important that the investigator assess not only the possible role of the IMP but also other potential contributing factors. Factors for consideration of the underlying cause may include:

- Medical and disease history.
- Lack of efficacy/worsening of treated condition.
- Concomitant or previous treatment.
- Withdrawal of IMP.
- Protocol-related procedure.

12.6 Reporting Procedures for All Adverse Events

All AEs (including SAEs) occurring during the study will be reported on the running logs in the AE section of the CRF. This includes all events from the time following screening (Visit 1) up to and including the post-study follow-up visit (Visit 12 or OLE Follow-up), whether or not attributed to IMP and observed by the investigator or patient.

The following information will need to be provided for all AEs:

A) Adverse Event (Diagnosis or Syndrome if Known, or Signs and Symptoms)

Where the investigator cannot determine a diagnosis, signs or symptoms should be recorded in the AE section of the CRF. Once a diagnosis has been determined the AE section of CRF must be updated to reflect the diagnosis in replacement of the original symptoms. In circumstances where only a provisional diagnosis is possible (working diagnosis), the CRF must be updated to reflect the provisional diagnosis in replacement of the original symptoms. In some circumstances it may be relevant for the investigator to include the symptoms alongside the diagnosis in the verbatim event description. However, the diagnosis (full or provisional) should be clearly stated (e.g., *headache and fever due to pneumonia*).

Study Code: GWEP1521
EudraCT Number: 2015-002154-12
Protocol V8 23Apr19

B) Adverse Event Start Date and Stop Date

The start and stop dates of the event must be provided. All AEs require these fields to be completed in full. Partial dates or missing dates are not normally acceptable and significant effort must be undertaken to obtain any unknown information. If a precise date is not known an estimated date should be provided instead. When a complete date cannot be given then record as much information as possible (i.e., month and year or, in exceptional circumstances, just year). When the actual start date becomes known the CRF must be updated to replace the previously recorded date.

C) Outcome

The outcome of the event must be recorded accurately and classified into one for the following categories:

- Recovered.
- Recovered with sequelae.
- Continuing.
- Patient died.

D) Severity

When describing the severity of an AE the terms mild, moderate, or severe should be used. Clinical judgment should be used when determining which severity applies to any AE.

If the severity of an AE fluctuates day-to-day, e.g., a headache or constipation, the change in severity should not be recorded each time; instead, only the worst observed severity should be recorded with AE start and stop dates relating to the overall event duration, regardless of severity.

A severe AE is not the same as a SAE. For example, a patient may have severe vomiting but the event does not result in any of the SAE criteria above. Therefore, it should not be classed as serious.

E) Causality

See [Section 12.5](#) above.

F) Action Taken with Study Medication

This question refers to the action taken with the IMP due to an AE. The action with the IMP must be classed as:

Study Code: GWEP1521
EudraCT Number: 2015-002154-12
Protocol V8 23Apr19

- None.
- Dose reduced temporarily.
- Dose reduced.
- Study medication interrupted.
- Study medication stopped.

12.7 Follow-up Procedures for Adverse Events

The investigator may be asked to provide follow-up information to the GW PVD for any AEs reported or during the investigation of potential safety issues. Such requests for additional safety information may occur post Visit 11 or OLE Follow-up after the study.

AEs considered related to the IMP by the investigator or the sponsor should be followed up until resolution or the event is considered stable.

It will be left to the investigator's clinical judgment whether or not an AE is of sufficient severity to require the patient's removal from treatment. A patient may also voluntarily withdraw from treatment due to what he or she perceives as an intolerable AE. Further details of withdrawal are presented in [Section 10](#). If either of these occurs, the patient must undergo an end of treatment assessment and be given appropriate care under medical supervision until symptoms cease or the condition becomes stable. If a safety concern is identified following withdrawal of a participant, GW may contact the investigator for additional follow-up information.

12.8 Potential Cases of Drug-induced Liver Injury

All investigational centers are required to submit to the GW PVD the laboratory results for any patient after randomization that meet the criteria for the selected laboratory parameters as follows:

- ALT or AST $> 3 \times$ ULN with the appearance of fatigue, nausea, vomiting, right upper quadrant pain or tenderness, fever, rash, and/or eosinophilia ($> 5\%$).
- ALT or AST $> 8 \times$ ULN.
- ALT or AST $> 5 \times$ ULN for more than two weeks.
- ALT or AST $> 3 \times$ ULN **and** (TBL $> 2 \times$ ULN **or** INR > 1.5).

Study Code: GWEP1521
EudraCT Number: 2015-002154-12
Protocol V8 23Apr19

These reports must be sent to the GW PVD using the same fax number for SAE reporting within 24 hours of becoming aware of the results. In addition, please send a copy of the patient's baseline laboratory results with all reports to the GW PVD.

Abnormal values in AST and/or ALT concurrent with abnormal elevations in TBL that meet the criteria outlined above are considered potential cases of drug-induced liver injury and will be considered as protocol defined criteria for withdrawal and important medical events. The investigator will arrange for the patient to return to the investigational site as soon as possible (within 24–48 hours of notice of abnormal results) for repeat assessment of ALT, AST, TBL, alkaline phosphatase and gamma-glutamyl transferase, detailed history and physical examination. Patients should be followed in this way until all abnormalities have normalized (in the investigator's opinion) or returned to the baseline state; however, if the above transaminase elevation criteria are confirmed by the first set of follow-up laboratory tests, the patient must be withdrawn from the trial.

Elevations in ALT or AST $> 3 \times \text{ULN}$ or TBL $> 2 \times \text{ULN}$ alone are not considered potential cases of drug-induced liver injury, but will be followed as detailed above, within 72 hours' notice of abnormal results. If the participant cannot return to the investigational center, repeat assessments may be done at a local laboratory and the results sent to GW PVD.

12.9 Notification of Safety Information to Investigators, Regulatory Authorities and Ethics Committees.

In accordance with the EU Clinical Trials Directive⁶⁰, relevant parts of the FDA Code of Federal Regulations⁶² and any national regulations, GW will inform investigators, Regulatory Authorities and relevant ECs/IRBs of all relevant safety information. This will include the reporting of relevant SAEs and all Suspected Unexpected Serious Adverse Drug Reactions (SUSARs).

This information will be provided through three sources:

- 1) IB: a compilation of the clinical and non-clinical safety data available on the IMP that is relevant to the study. The IB is updated annually.
- 2) Development Core Safety Information: this document forms the safety section of the IB⁵¹, or is updated as an addendum to the IB⁵¹. This document is revised if necessary, when new important safety information becomes available (potentially up to a few times a year).

Study Code: GWEP1521
EudraCT Number: 2015-002154-12
Protocol V8 23Apr19

- 3) Council for International Organizations of Medical Sciences (CIOMS) reports: these reports are issued every time a SUSAR is reported to GW. They provide information on individual case reports and are sent to all the Regulatory Authorities, the relevant central ECs/IRBs which have approved the study and investigators. As required, the investigator should notify their regional ECs/IRBs of SAEs or SUSARs occurring at their center and other AE reports, i.e., CIOMS reports and any additional safety documentation received from GW, in accordance with local procedures.

In the USA, investigators are normally required to promptly report to their IRBs all unanticipated problems involving risks to human patients, or others, including AEs that should be considered unanticipated problems. Based on current FDA guidance⁵⁷ the following clarification is provided in determining what constitutes an unanticipated problem:

In general, an AE observed during the conduct of a study should be considered an unanticipated problem involving risk to patients and reported to the IRB, *only* if it were unexpected, serious, and would have implications for the conduct of the study (e.g., requiring a significant, and usually safety-related, change in the protocol such as revising inclusion/exclusion criteria or including a new monitoring requirement, informed consent/assent, or IB). An individual AE occurrence *ordinarily* does not meet these criteria because, as an isolated event, its implications for the study cannot be understood.

In The Netherlands, all SAEs observed during the conduct of a study will be reported within the stipulated timelines to the De Medisch Ethische Toetsingscommissie/Centrale Commissie Mensgebonden Onderzoek *only* if it were considered an unanticipated problem involving risk to patients and would have implications for the conduct of the study (e.g., requiring a significant, and usually safety-related, change in the protocol such as revising inclusion/exclusion criteria or including a new monitoring requirement, informed consent/assent, or IB). All other SAEs will be reported in a cumulative summary as part of the Development Safety Update Report and updated on a yearly basis. This does not replace the ongoing obligation to report any SUSARs originating in The Netherlands, which do not meet the above criteria, to the accredited Medical Research Ethics Committee and competent authority.

The FDA guidance⁶² states that, accordingly, to satisfy the investigator's obligation to notify the IRB of unanticipated problems, any investigators participating in a

Study Code: GWEP1521
EudraCT Number: 2015-002154-12
Protocol V8 23Apr19

multicenter study may rely on the sponsor's assessment and provide to the IRB a report of the unanticipated problem prepared by the sponsor.

GW will inform investigators, Regulatory Authorities and relevant ECs/IRBs of any safety issues or case reports that are considered to be unanticipated and provide such reports as mentioned above. It should be noted that a single SUSAR report notified to investigators in the study does not necessarily constitute an unanticipated problem unless identified by GW in the submission cover letter.

As a minimum, the recipient will be sent all of the above and relevant updates between the period from ethical approval and final database lock.

Study Code: GWEP1521
EudraCT Number: 2015-002154-12
Protocol V8 23Apr19

13 STATISTICAL CONSIDERATIONS

A statistical analysis plan (SAP) will be produced prior to unblinding of the study. Any deviations from the original SAP will be described in the final clinical study report.

13.1 Sample Size, Power and Significance Levels

Blinded Phase:

A total of 210 patients will be enrolled. The 210 patients will be randomly allocated to one of four treatment groups (GWP42003-P 25 mg/kg/day, GWP42003-P 50 mg/kg/day, placebo 25 mg/kg/day dose volume equivalent, or placebo 50 mg/kg/day dose volume equivalent) at a 2:2:1:1 ratio. The placebo groups will be pooled for the analyses of efficacy.

If it is assumed that patients in the placebo group will experience a mean reduction in seizure frequency of 15% (from baseline), patients receiving GWP42003-P will experience at least a 50% reduction in seizures and a common standard deviation of 60%, then this sample size of 70 patients per group will be sufficient to detect a difference in response distributions with 90% power. This test is based on a two-sided non-parametric Wilcoxon-Mann-Whitney test for continuous response data with a 5% significance level.

Open-label Extension:

All patients who wish to continue on IMP following the blinded phase.

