13.6 Endpoints and Statistical Methods

Blinded Phase:

Statistical hypothesis testing will be performed on the primary endpoint and other endpoints as appropriate. Each endpoint, including the primary will have 2 comparisons against placebo (25 mg/kg/day GWP42003-P and 50 mg/kg/day GWP42003-P vs. placebo). Also, 3 key secondary endpoints have been defined.

Study Code: GWEP1521
 EudraCT Number: 2015-002154-12
 Protocol V8 23Apr19

The primary and key secondary endpoints will be tested with their Type I error controlled by use of a hierarchical gate-keeping procedure, in the sequence given in Table 13.6-1. One must reject the null hypothesis of an endpoint at the level of 0.05 (2-sided) to test the hypothesis of the subsequent endpoint in the sequence at the level of 0.05 (2-sided). If a null hypothesis is not rejected then testing will stop and all subsequent analyses will be declared not statistically significant.

Test	Endpoint	Treatment Comparison
1	Change from baseline in number of TSC-associated seizures	25 mg/kg/day GWP42003-P vs. Placebo
2	50% responder analysis	25 mg/kg/day GWP42003-P vs. Placebo
3	Change from baseline in number of TSC-associated seizures	50 mg/kg/day GWP42003-P vs. Placebo
4	50% responder analysis	50 mg/kg/day GWP42003-P vs. Placebo
5	Change in CGIC/SGIC	25 mg/kg/day GWP42003-P vs. Placebo
6	Change from baseline in total seizures	25 mg/kg/day GWP42003-P vs. Placebo
7	Change in CGIC/SGIC	50 mg/kg/day GWP42003-P vs. Placebo
8	Change from baseline in total seizures	50 mg/kg/day GWP42003-P vs. Placebo

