13.6.2 Primary Endpoint(s)

Blinded Phase:

The primary endpoint is the change in number of seizures* during the treatment period (maintenance and titration) compared to baseline in patients taking GWP42003-P compared with placebo.

*Seizures include: focal motor seizures without impairment of consciousness or awareness; focal seizures with impairment of consciousness or awareness; focal seizures evolving to bilateral generalized convulsive seizures and generalized seizures (tonic-clonic, tonic, clonic or atonic) that are countable.

Data will be analyzed using negative binomial regression on the sum of the seizure counts during the treatment period. However, seizure frequency (average per 28 days) and percentage change in seizure frequency will be presented using summary statistics. A mixed effect model with repeated measures will be performed modelling the observed number of seizures in the baseline period and treatment period implemented within the framework of general linear models using the negative binomial response distribution. The model will include stratified age group (1–6 years, 7–11 years, 12–17 years and 18–65 years), time, treatment arm and treatment arm by time interaction as fixed effects and patient as a random effect. The log transformed number of days in which seizures were reported will be included as an offset. The time variable corresponds to an indicator for the baseline period and treatment period. The estimated ratio of least squares means for treatment period to baseline period and 95% confidence intervals (CIs) will be presented for each treatment arm. In addition, the estimated ratio of each GWP42003-P group to placebo and 95% CIs will be presented along with the p-value testing the null hypothesis that this ratio is 1.

The hypothesis testing approach for controlling the Type I error is described in [Section 13.6](#) and [Table 13.6-1](#).

If a patient withdraws from the study, then the primary analysis variable will be calculated from the available data, during the treatment period, prior to the patient withdrawing.

Open-label Extension:

The primary endpoint is the safety of GWP42003-P, evaluated by assessing the incidence, type and severity of AEs. Data will be presented as per [Section 13.6.5.2](#).

Study Code: GWEP1521
 EudraCT Number: 2015-002154-12
 Protocol V8 23Apr19

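### The 90% power in Section 13.1 is a stand-alone Wilcoxon figure: it describes neither the current primary model nor the gated 50 mg/kg/day primary comparison

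*Protocol*

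**What the plan says.** Section 13.1 assumes a mean reduction in seizure frequency of 15% on placebo and at least 50% on GWP42003-P, with a common SD of 60%. It concludes "then this sample size of 70 patients per group will be sufficient to detect a difference in response distributions with 90% power" and adds: "This test is based on a two-sided non-parametric Wilcoxon-Mann-Whitney test for continuous response data with a 5% significance level". It makes no distinction between the doses and does not mention the order of testing. Allocation is 2:2:1:1, and "The placebo groups will be pooled for the analyses of efficacy". The same statement stands in the synopsis and in Section 4.3, which refers the reader to Section 13.1 for the full explanation of the calculation.

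Section 13.6.2 names a different primary test: "Data will be analyzed using negative binomial regression on the sum of the seizure counts during the treatment period", implemented as a mixed model on the baseline and treatment-period counts. Section 13.6.2.1 lists the Wilcoxon test on percentage change as a sensitivity analysis.

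Section 13.6 gives the primary endpoint two comparisons with placebo and places them in a fixed sequence, each test at two-sided 0.05. In Table 13.6-1 the order begins:

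1. 25 mg/kg/day, primary endpoint
2. 25 mg/kg/day, 50% responder analysis
3. 50 mg/kg/day, primary endpoint
4. 50 mg/kg/day, 50% responder analysis

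The stopping rule is explicit: "If a null hypothesis is not rejected then testing will stop and all subsequent analyses will be declared not statistically significant".

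**The concern.** A reader of Section 13.1 will take 90% as the chance that the primary analysis succeeds for an effective dose, and Section 3.4 states the primary hypothesis for the dose groups in the plural. Neither part of that reading fits the current plan. The test behind the 90% no longer produces the primary p-value, and the 50 mg/kg/day primary result can be claimed only after two other tests have succeeded, one of them on a binary endpoint.

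The amendment history shows how this arose. Amendment 4 replaced a Hochberg procedure on the two primary comparisons with a fixed sequence. It reworded the power sentence in Section 4.3 to name the Wilcoxon test but took no account of the sequence. Amendment 6 replaced the Wilcoxon test with the negative binomial model and left the power statement alone. Amendment 7 reordered the sequence, again without revisiting power.

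At stake is the stated chance of a formal claim for the second primary comparison. An effective 50 mg/kg/day arm can end as not statistically significant because the 25 mg/kg/day responder test missed 0.05, and the sample size section gives no sign that this is likelier than one time in ten.

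**Working it through.** **Inputs from the protocol.** Mean reductions 15% and 50%, SD 60%, two-sided 5% (Section 13.1). Group size: 210 × 2/6 = 70 per active arm, and 35 + 35 = 70 pooled placebo. Test order: Table 13.6-1.

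**Assumptions added here.** Percentage change is normal; both doses have the same 50% mean reduction; Wilcoxon is used for tests 1 and 3; test 2 is an unstratified Mantel–Haenszel chi-square on a reduction of 50% or more (the protocol stratifies by age).

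**Step 1: reproduce the 90%.** Noether's formula for a two-group Wilcoxon test:

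- p = Φ(35 / (60√2)) = 0.660
- power = Φ(√(12 × 0.25 × 140) × (0.660 − 0.5) − 1.96) = 90.6%
- 68.4 patients per group are needed for exactly 90%

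The stated figure is therefore correct for one stand-alone comparison.

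**Step 2: gate test 3 behind test 1 only.** Two comparisons that share an equal-sized placebo arm have test statistics correlated at 0.5. If each has 90% power, the probability that both succeed is Φ₂(1.28, 1.28; 0.5) = 83.2%. This uses no responder assumption.

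**Step 3: power of the responder gate.** Under the normal assumption:

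- active rate 50%; placebo rate Φ(−35/60) = 0.2798; mean of the two 0.390
- pooled SE = √(2 × 0.390 × 0.610 / 70) = 0.0824
- unpooled SE = √((0.2798 × 0.7202 + 0.25) / 70) = 0.0803
- power = Φ((0.2202 − 1.96 × 0.0824) / 0.0803) = 76.7%

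**Step 4: the sequence.** Simulation of 40,000 trials with three arms of 70 and a shared placebo arm:

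| Event | Probability |
|---|---|
| Test 1 significant | 91.7% |
| Test 2 significant | 76.7% |
| Tests 1 and 2 both significant | 75.9% |
| Tests 1, 2 and 3 all significant | 72.1% |

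A second run gave 71.6% for the last row. With 66 per group, where the simulated Wilcoxon power is almost exactly 90%, it is 68.4%. Making the 50 mg/kg/day effect so large that test 3 never fails raises the result only to 75.7%, so the gate sets the limit.

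**Step 5: how far the answer moves.** The protocol states no responder rates. Power of test 2 against an active rate of 50%:

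| Placebo responder rate | Power of test 2 |
|---|---|
| 22% | 94% |
| 25% | 87% |
| 28% | 77% |
| 30% | 68% |

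Holding the means and SD but changing the shape, the probability that tests 1 to 3 all succeed is 50% (uniform) and 80% (logistic). It is 97.6% (gamma) and 99.7% (lognormal) when the remaining seizure frequency is skewed. The two skewed models give test 1 a power of 99.7% or more, so they do not reproduce the sponsor's 90%. The normal model does, but it places 1 − Φ(50/60) = 20% of active patients above a 100% reduction, which is impossible.

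**Step 6: the current primary model.** Its power cannot be computed from the protocol, which states no dispersion.

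**The case against.** The strongest reply is that Section 13.1 does what sample size sections usually do: it gives the power of one comparison, for a named test, at a named level. It never promises 90% for the sequence, and the figure reproduces. That stands. A reader might infer an arithmetic error; there is none. The fault is that the statement no longer matches the analysis and testing sections.

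Second, a reader might take 72% as the true power for 50 mg/kg/day. The documents do not support that. The figure needs a distribution and responder rates that the protocol does not give, and it uses the superseded Wilcoxon test for tests 1 and 3. What survives is the direction: if each primary comparison has 90% power alone and the doses work equally well, test 3 cannot keep 90% behind test 1, and the responder gate can only lower it further.

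Third, a reader might infer that test 1 is underpowered under the new model. Nothing shows this. The Amendment 6 rationale, drawing on earlier epilepsy trials, expects the model may have more power. But greater power for the primary model does not lift the responder gate, which under the normal assumption caps test 3 near 77%.

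Fourth, a reader might conclude that tests 2 and 3 should be swapped. The order is a disclosed choice: Amendment 7 moved the 50 mg/kg/day primary from fifth to third so that all TSC-associated seizure endpoints, responders included, come first. A swap would help one claim at the expense of another, and Type I error is controlled either way.

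**Conclusion.** The point holds as an inconsistency within the protocol. The 90% is valid for one stand-alone Wilcoxon comparison, but that test is now a sensitivity analysis and the second primary comparison is no longer tested on its own. For 50 mg/kg/day, the chance of a formal primary claim falls from 90% to about 83% through test 1 alone, given equal dose effects. It falls to about 72% once the responder gate is added, given normal percentage change and the stated means and SD. The first step rests on little beyond the shared placebo arm and equal effects. The second is illustrative: 50% to 80% under other symmetric shapes, and higher if the placebo responder rate is below 28%. The trial's validity and error control are unaffected. The statistical analysis plan was not available, but Section 4.3 treats Section 13.1 as the complete account, so the correction belongs in the protocol.

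**What to change.** In Section 13.1, Section 4.3 and the synopsis:

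1. State that 90% is the stand-alone, per-comparison Wilcoxon power and applies to test 1 of Table 13.6-1 only.
2. Recompute the power of the primary analysis for the negative binomial mixed model, over a stated dispersion range taken from the earlier trials cited in Amendment 6.
3. Give the power of test 3 within the sequence under that model, with the assumed responder rates written out and the result shown as a range, not as a fixed 72%.

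The cost is a few sentences and a short simulation before unblinding, using data the sponsor says it has already explored. The figure for 50 mg/kg/day is likely to look less favourable than the one now printed. Sample size, analyses and order of tests can stay as they are.
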